## 4.2.3 ViscoPass Study (Initial Phase)

During the Dose Selection Phase of this study, 62 subjects were randomized using a 1:1:1 schedule to receive either CyPass Micro-Stent with 30 µl of adjunct Healon viscoelastic, CyPass Micro-Stent with 60 µl of adjunct Healon viscoelastic, or the CyPass Micro-Stent with no adjunct Healon viscoelastic.

With 6 months follow-up on all subjects, there was no difference in safety among the three arms, and the 60  $\mu$ l arm had a comparable rate of AEs to either the Cypass only arm or the 30  $\mu$ l arm. Also, there were no unanticipated or vision-threatening adverse events in either group. Additionally, there was a trend towards higher efficacy with the 60  $\mu$ l arm compared to the other two arms for the primary and secondary efficacy outcomes.

Based on the results of the initial phase and considering the risk-benefit profile of each arm, the 60  $\mu$ l arm was selected as the go-forward dose with recommended discontinuation of the 30  $\mu$ l arm which had no appreciable benefit in either safety or efficacy.

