## 8. STATISTICAL METHODS

#### 8.1 Sample Size

The primary effectiveness endpoint is the outcome of  $\geq 20\%$  decrease in IOP from baseline without IOP lowering medications up to 12 months post-operatively (IOP response). The proportion of eyes meeting the effectiveness outcome, IOP response rate, will be assessed at 12 months. A sample of at least 101 eyes will be enrolled across the two groups (CyPass only control and CyPass + Healon 5 dose selected) with an estimated 86 eyes completing their month 12 visit. Assuming a 30% success rate for the control eyes and a 60% success rate for the visco-assisted eyes, 80% power can be achieved with 43 eyes per arm using a two-tailed alpha of 0.05.

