1.2 Study Description

This is a prospective, randomized, controlled, multicenter, interventional study performed in two phases, as stated below. Up to 150 eyes meeting subject eligibility criteria listed in Section 6 of the protocol will be randomized to study treatment at up to 10 investigational sites.

Note, only one eye per subject may be treated under the study protocol. If both eyes qualify for the study, the study investigator will choose which eye will be the study eye. Unless specified otherwise, ocular results refer to the study eye only. Therefore, throughout this SAP and corresponding tables and data listings, the number of subjects and eyes are synonymous.

Dose Selection Phase: During this phase, the first cohort (Cohort 1) of 63 subjects was randomized (1:1:1) to receive either a CyPass Micro-Stent with 30 μl adjunct Healon 5 viscoelastic, a CyPass Micro-Stent with 60 μl of adjunct Healon 5 viscoelastic, or a CyPass Micro-Stent without adjunct viscoelastic. After completion of at least 3 months follow-up on all subjects in this phase, an interim review of safety and efficacy data was performed to determine the optimum dose of adjunct viscoelastic for the study expansion phase.

Expansion Phase: After the dose selection phase, the study was expanded to include a second cohort (Cohort 2) of up to 90 additional subjects who were randomized 1:1 to either the CyPass Micro-Stent without adjunct viscoelastic or to the CyPass Micro-Stent with 60 μ l adjunct viscoelastic (the dose selected based on Dose Selection Phase results).

Visit Schedule and Visit Windows: Enrolled study subjects are expected to participate in the study from Screening/Baseline through 12 months postoperatively in accordance with Table 1 – Study Examinations and Procedures (Appendix 1 in the study protocol) below.

Note, prior to protocol version D, Amendment dated 07Oct2014, the 12 Month Washout visit was not required for mainly the initial dose selection phase subjects who were on IOP lowering medication. All Cohort 2 patients were enrolled under protocol version D or a later version.

Version: 2.0; Most-Recent; Effective; CURRENT

Status: Effective

Document: TDOC-0053376 Version: 2.0; Most-Recent; Effective; CURRENT

Status: Effective

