6.3.11 Device Deficiencies

The applicable definition of a device deficiency is in the study protocol. A listing of all device deficiencies, as recorded on the Device Deficiency Log, will be provided.

7 Sample Size and Power Calculations

The primary effectiveness endpoint is the outcome of \geq 20% decrease in IOP from baseline without IOP lowering medications up to 12 months post-operatively (IOP response). The proportion of eyes meeting the effectiveness outcome, IOP response rate, will be assessed at 12 months. A sample of at least 101 eyes will be enrolled across the two groups (CyPass only control and CyPass + Healon 5 dose selected) with an estimated 86 eyes completing their month 12 visit. Assuming a 30% success rate for the control eyes and a 60% success rate for the visco-assisted eyes, 80% power can be achieved with 43 eyes per arm using a two-tailed alpha of 0.05 that is based on the Likelihood Ratio Chi-square test for two proportions. It is

Document: TDOC-0053376 Version: 2.0; Most-Recent; Effective; CURRENT

Status: Effective

estimated that approximately 10% of those receiving the CyPass Micro-Stent may be lost to follow-up.

Document: TDOC-0053376 Version: 2.0; Most-Recent; Effective; CURRENT

Status: Effective

Date/Time (mm/dd/yyyy GMT):	Signed by:	Justification:
05/29/2017 11:06:02		
05/30/2017 18:23:03		
06/05/2017 20:12:51

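### Do the sample-size figures need correcting because 101 eyes, 86 completers and 10% loss do not line up, and because Cohort 1 is given as both 62 and 63?

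*SAP*

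**What the plan says.** SAP section 7 and Protocol 8.1 give the same sizing: "A sample of at least 101 eyes will be enrolled across the two groups" (stent alone, and stent with the selected viscoelastic dose), with an estimated 86 eyes completing Month 12. The design assumption is "Assuming a 30% success rate for the control eyes and a 60% success rate for the visco-assisted eyes", under which "80% power can be achieved with 43 eyes per arm using a two-tailed alpha of 0.05". The SAP adds that this is "based on the Likelihood Ratio Chi-square test for two proportions". On attrition, SAP section 7 says it is "estimated that approximately 10% of those receiving the CyPass Micro-Stent may be lost to follow-up", and Protocol section 5 gives the same estimate.

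On cohort sizes, the protocol plans 60 subjects for Cohort 1 (sections 2.3 and 5). Its section 4.2.3, looking back on that phase, says "62 subjects were randomized using a 1:1:1 schedule". SAP 1.2 says "the first cohort (Cohort 1) of 63 subjects was randomized (1:1:1". Both documents allow up to 90 in Cohort 2 and up to 150 in total; SAP 1.2 words the total as "Up to 150 eyes meeting subject eligibility criteria".

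**The concern.** Three numbers in one paragraph of SAP section 7 (101, 86 and 10%) look as though each should follow from the others, and they do not. A reader may suspect that the inflation for dropout was miscalculated, or that the attrition assumption was changed without redoing the sum. If so, the trial could be wrongly sized.

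The Cohort 1 counts raise a different worry. Both 62 and 63 are reported in the past tense as numbers randomised in the same phase. A subject who appears in one count and not the other might have been left out of the interim review or of the final analysis. The SAP's 63 plus up to 90 also exceeds its own ceiling of 150, which the original 60 plus 90 met exactly.

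**Working it through.** **Inputs.** Response rates 0.30 and 0.60, two-sided alpha 0.05, 80% power, 43 per arm, likelihood-ratio chi-square test, 101 enrolled, 86 completers, about 10% lost (SAP section 7). Cohort 1 of 60 planned (Protocol 2.3), and 62 (Protocol 4.2.3) or 63 (SAP 1.2) randomised. Ceilings of 90 and 150 (SAP 1.2).

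**1. The plan's own figure.** For *n* per arm and mean rate 0.45, the noncentrality of the likelihood-ratio test is

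G = 2n × {[0.3 ln(0.3/0.45) + 0.7 ln(0.7/0.55)] + [0.6 ln(0.6/0.45) + 0.4 ln(0.4/0.55)]} ≈ 0.1848 n,

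and power ≈ Φ(√G − 1.96).

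| n per arm | Power |
|---|---|
| 42 | 79.6% |
| 43 | 80.5% |
| 45 | 82.2% |

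So 43 is the smallest number reaching 80%, as stated. Exact enumeration of the same test at 43 per arm gives 81.0%.

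**2. From completers to enrolled eyes.**

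- Implied total loss: 1 − 86/101 = 14.9%.
- At 10% loss, eyes needed for 86 completers: 86/0.90 = 95.6, so 96.
- At 10% loss, completers from 101 eyes: 101 × 0.90 = 90.9, about 91 (45 per arm).
- At 15% loss: 86/0.85 = 101.2, which matches 101.

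The enrolled figure therefore behaves like a 15% allowance.

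**3. Whether 10% and 14.9% measure the same thing.** The 10% has implanted eyes as its base and counts only loss to follow-up. The step from 101 to 86 starts from enrolled eyes, and both documents define enrolment as signing consent (Protocol 7.1; SAP section 2). It ends at completion of Month 12. Protocol 7.6.1 lists other exits: screen failure, adverse events, voluntary withdrawal, and surgery in which the stent is not placed. If 10% of implanted eyes are lost, 86 completers correspond to 96 implanted eyes, leaving 101 − 96 = 5 eyes (5/101 = 5.0%) for everything else. That remainder is not itemised, but it is not impossible.

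**4. Direction of the mismatch.** If the 10% is right for all losses, 101 eyes yield about 45 per arm and 82.2% power rather than 80.5%. The larger enrolment figure errs on the safe side.

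**5. Cohort totals.** 60 + 90 = 150; 62 + 90 = 152; 63 + 90 = 153. Both 90 and 150 are upper limits. With 63 in Cohort 1, the overall limit leaves 150 − 63 = 87 for Cohort 2. At 1:1:1, about 21 of the 63 are in the 30 µl arm, so 42 count towards the comparison. The two arms then have room for 42 + 87 = 129 eyes, well above 101.

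**6. The 62/63 count.** SAP 2.1 defines the full analysis set as all randomised subjects who undergo implantation surgery, analysed as randomised. SAP 4.1 requires subject accountability and counts of each analysis set by site and treatment. Those numbers come from the database, not from the narrative in SAP 1.2 or Protocol 4.2.3.

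**The case for a change.** The strongest case for a correction is that the broad reading of enrolled is strained. The 101 eyes are placed in the two treatment groups, and groups exist only after randomisation, which happens on the day of surgery (Protocol 7.2; SAP 1.3). Subjects who exit at screening or baseline are replaced (Protocol 7.1), so they should not use up the allowance. No other source of loss is quantified. On that reading, about five percentage points of attrition are undocumented. Likewise, a cohort already reported with six months of follow-up on all subjects should not gain a member. The SAP updated 60 to 63 without adjusting the limits beside it.

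Much of this stands as description. Neither document explains how 101 becomes 86, and the supplied documents do give two counts for one event. What does not stand is any consequence. The 62 comes from protocol Version D, while the SAP follows Version F, which is not among the documents supplied; other details also differ between the two documents, such as 5 sites against 10. The number may already agree in Version F, and that cannot be checked here. The 60 is a plan, not a rival count. Two upper limits that do not add up show no overrun, because the tighter one applies.

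**Conclusion.** No change to the plan is called for. The unexplained part of the attrition allowance is about five eyes in 101. It leaves the 43 per arm and its 80.5% power untouched and, if anything, gives slightly more power (about 82% at 10% total loss). The Cohort 1 difference is one subject between documents of different generations; the rule-based analysis sets and the accountability tables in SAP 4.1 settle it from the data. The ceilings are compatible, and they leave room for 129 eyes in the two compared arms.

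This rests on the stated rates of 30% and 60%, on an even three-way split of 63 in Cohort 1, and on reading the 10% as the text words it, as loss to follow-up after implantation. If the 10% was instead meant to cover all losses, the slip is clerical and conservative. Either way, following the documents as written gives the same sample, the same analysis and the same conclusion.
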